#### 4.3.3 Sensitivity Analyses

Not applicable.

## 4.3.4 Supplementary Analyses

Not applicable.

#### 4.4 Tertiary/Exploratory/Other Endpoints Analysis

Not applicable.

# 4.5 Other Safety Analyses

#### 4.5.1 Extent of Exposure

Treatment duration will be defined as the number of days from the day of first study intervention intake up to and including the day of last study intervention intake excluding any gaps in study intervention intake (according to exposure data from the eCRF) and will be summarized using descriptive statistics.

The total intervention dose (according to drug accountability data from the eCRF) will be summarized in mg per day using descriptive statistics.

Compliance (as percentage) will be calculated as follows:

number of tablets actually taken / number of tablets planned to be taken \* 100.

The number of tablets planned to be taken is one tablet per study day based on the planned two-week intervention period. It is 14 at least but considering the allowed extension by up to four days, the denominator will be calculated as

max(14, date of final visit - date of first intervention intake <math>+ 1).

Participants ending the study before day 14 will have a compliance below 100%.

The compliance will be summarized descriptively. In addition, percent of compliance will be categorized into >100%, =100% and <100% and these categories will be summarized descriptively as well.

Version 1.0 Page: 12 of 15

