6.1 Study Intervention Administered

Study intervention should be taken orally with food at the same time each day, preferably in the morning. If a dose is missed, it should be taken as soon as the participant remembers on the same day of the missed dose. But there should be consistency with respect to dosing intervals (the recommendation is to have at least a 20-hour interval between doses). Participants should not take 2 doses of study intervention on the same day. The investigator should be informed if the dose of Vericiguat taken has exceeded the scheduled dose.

Intervention Label	Vericiguat
Intervention Name	Vericiguat
Intervention Description	Tablet 5 mg/day
Type	Small molecule drug
Dose Formulation	Tablet
Unit Dose Strength(s)	5 mg
Dosage Level(s)	1 x 5 mg daily for 14 (+4) days
Route of Administration	Oral
Use	Experimental
Sourcing	Vericiguat will be provided centrally by the Sponsor.
Packaging and Labeling	Vericiguat tablets are available in high density polyethylene (HDPE) bottles with a white child resistant closure and induction seal. The packaging configuration is 18 tablets Vericiguat 5 mg per bottle. The bottles will be labelled as required per country requirement.
Current/Former Name(s) or Alias(es)	VERQUVO®, BAY 1021189

Table 6-1: Study Intervention Administered

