6.5 Study Intervention Compliance

A participant will receive exactly one bottle of vericiguat 5 mg tablets containing 18 tablets for any unforeseen events (e.g. loss or damage of single tablets or to allow for visit window).

Compliance with study intervention (vericiguat) self-administered at home between Visit 1 and Visit 2, will be assessed at Visit 2 (Day 14). Compliance will be assessed by counting returned tablets during the site visit and documented in the source documents and relevant form.

Deviation(s) from the prescribed dosage regimen should be recorded. Any discrepancies between actual and expected amount of returned study intervention must be discussed with the participant at the time of the visit, and any explanation must be documented in the source records. An adequate record of receipt, distribution, and return/destruction of all study intervention must be kept.

A record of the quantity of vericiguat tablets dispensed to and administered by each participant must be maintained and reconciled with study intervention and compliance records. An adequate record of receipt, distribution, and return/destruction of all study intervention must be captured on the dispensing log and/or in the IRT. Intervention start and stop dates, including dates for intervention delays will also be recorded in the CRF/eCRF.

Participants will be instructed to take study intervention as scheduled, and to return all of the study intervention packaging including unused study intervention and empty packaging.

29 NOV 2023 Page: 22 of 44

Study intervention tablets not returned will be considered to have been taken unless otherwise specified. At the end of the study, any remaining study intervention will be collected and destroyed as per local regulations. Any discrepancies between the returned and expected returned study intervention should be explained.

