7.3 Lost to Follow Up

A participant will be considered lost to follow-up if the participant fails to return for Visit 2 and is unable to be contacted by the study site.

The following actions must be taken if a participant fails to return to the clinic for a required study visit:

29 NOV 2023 Page: 25 of 44

- The site must attempt to contact the participant and reschedule the missed visit as soon as possible, counsel the participant on the importance of maintaining the assigned visit schedule, and ascertain whether the participant wishes to and/or should continue in the study.
- Before a participant is deemed lost to follow up, the investigator or designee must
 make every effort to regain contact with the participant (where possible, 3 telephone
 calls, and if necessary, a certified letter to the participant's last known mailing address
 or local equivalent methods). These contact attempts should be documented in the
 participant's medical record.
- Should the participant continue to be unreachable, the participant will be considered lost to follow up.

8. Study Assessments and Procedures

- Study procedures and their timing are summarized in the SoA. Protocol waivers or exemptions are not allowed.
- Adherence to the study design requirements, including those specified in the SoA, is essential and required for study conduct.
- All screening evaluations must be completed and reviewed to confirm that potential participants meet all eligibility criteria. The investigator will maintain a screening log to record details of all participants screened and to confirm eligibility or record reasons for screening failure, as applicable.
- Procedures conducted as part of the participant's routine clinical management (e.g., local laboratory) and obtained before signing of the ICF may be utilized for screening or baseline purposes provided the procedures met the protocol-specified criteria and were performed within the timeframe defined in the SoA.
- In the event of a significant study-continuity issue (e.g. caused by a pandemic), alternate strategies for participant visits, assessments, medication distribution and monitoring may be implemented by the sponsor or the investigator, as per local health authority/ethics requirements.

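### The compliance denominator in SAP 4.5.1 has no ceiling at 18 tablets, so if a final visit falls after Day 18, full use of the supply is scored below 100%; only a descriptive summary is affected.

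*SAP*

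**What the plan says.** SAP 4.5.1 (Extent of Exposure) defines compliance as "number of tablets actually taken / number of tablets planned to be taken", times 100. It introduces the planned number with the words "It is 14 at least but considering the allowed extension by up to four days, the denominator will be calculated as" and then gives the formula "max(14, date of final visit - date of first intervention intake" plus 1). Compliance is summarised as a continuous percentage and also in three categories: above, exactly at and below 100%. The same section reports treatment duration (gaps excluded) and total dose in mg per day.

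The protocol supplies the matching limits. Table 6-1 gives one 5 mg tablet daily for 14 days plus up to four, and states "The packaging configuration is 18 tablets Vericiguat 5 mg per bottle". Section 6.5 says "A participant will receive exactly one bottle of vericiguat 5 mg tablets containing 18 tablets", partly to cover the visit window. No resupply is described. The Schedule of Activities (1.3) puts Visit 2 at Day 14 with a window of +4 days. Section 6.6.1, by contrast, describes treatment as running over Days 1 to 14.

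For a participant who misses a visit, Protocol 7.3 says: "The site must attempt to contact the participant and reschedule the missed visit as soon as possible". It sets no latest day.

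**The concern.** The sentence and the formula it introduces do not match. The sentence describes 14 to 18 planned tablets. The formula applies the lower limit and leaves the upper one out. After Day 18 the denominator goes on growing by one tablet a day, while the numerator cannot exceed the 18 tablets dispensed. The formula then counts as planned some tablets that the protocol neither schedules nor supplies, and a score of 100% can no longer be reached.

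The three categories have no tolerance band. One day beyond the window is therefore enough to move a participant who used the whole supply to below 100%. For such a participant the score reflects the date of the visit and not intake. At stake is how the exposure table is read.

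**Working it through.** **Inputs**
- D = study day of the final visit, with first intake on Day 1 at Visit 1 (Schedule of Activities), so D = final visit date − first intake date + 1.
- Tablets supplied: 18 (Protocol 6.1 and 6.5).
- At most one tablet a day (Protocol 6.1).
- Tablets not returned count as taken unless otherwise specified (Protocol 6.5), so the numerator is at most 18.

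**Step 1: reproduce the stated range.** The SAP denominator is max(14, D). For D = 14, 15, 16, 17 and 18 it gives 14, 15, 16, 17 and 18. Inside the window the formula does what the sentence describes, and daily intake up to the visit scores 100%.

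**Step 2: go past the window.** With all 18 tablets taken, the SAP score is 100 × 18 / max(14, D). The capped score is 100 × 18 / min(18, max(14, D)).

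| Final visit | SAP denominator | SAP score | Capped score |
|---|---|---|---|
| Day 18 | 18 | 100.0% | 100.0% |
| Day 19 | 19 | 18/19 = 94.7% | 100.0% |
| Day 20 | 20 | 18/20 = 90.0% | 100.0% |
| Day 21 | 21 | 18/21 = 85.7% | 100.0% |

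For D ≤ 18 the two denominators are identical, so the cap changes no in-window score.

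**Step 3: check the cap for a side effect.** Suppose a participant misses three doses in Days 1 to 18, takes the three remaining tablets on Days 19 to 21 and is seen on Day 21. By Day 18 they have taken 15 tablets.
- SAP formula: 18/21 = 85.7%.
- Cap on the denominator only: 18/18 = 100%, which hides three missed days.
- Cap plus numerator limited to Day 18: 15/18 = 83.3%.

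The cap therefore needs a matching limit on the numerator.

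**Step 4: an in-window case that the cap does not reach.** A participant dosed on Days 1 to 14 only, as Protocol 6.6.1 reads, has taken 14 tablets. If seen on Day 18, they score 14/18 = 77.8% under either denominator. This comes from the difference between 6.6.1 and Table 6-1, not from the missing ceiling.

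**The case against.** The strongest reply is that the formula is correct for every visit the protocol allows. Visit 2 has a +4 day window, and Protocol Section 8 requires adherence to the schedule and allows no waivers. A missed Day 14 visit can be rescheduled to Days 15 to 18. This stands. A reader might infer from Protocol 7.3 that visits after Day 18 are expected. The text does not support that: it leaves them possible, as deviations, and no more.

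A reader might also infer that the tolerability results are at risk. They are not. The primary and sensitivity analyses (SAP 4.2.1 to 4.2.3) rest on completing treatment with at most one or two days' interruption and on the absence of moderate to severe symptomatic hypotension. Of the secondary tolerability analyses (SAP 4.3.2.2), one is stated to be independent of compliance and the other uses continuous intake or restart. No analysis set or threshold uses the percentage, and neither treatment duration nor total dose uses this denominator.

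Nor would the below-100% category otherwise be a clean group of people who did not take the drug. A participant with the one permitted missed dose, seen on Day 14, scores 13/14 = 92.9% and belongs there, and SAP 4.5.1 itself says that participants who end before Day 14 score below 100%.

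What the reply leaves untouched is the mismatch itself. The SAP states an upper limit in words and omits it from the formula, and nothing else in either document says how an out-of-window visit enters the calculation.

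**Conclusion.** The formula is wrong as written, in a minor way. It matters only if a final visit falls after Day 18, and then only in the descriptive compliance summary.

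For a participant who took all 18 tablets the error is 5.3 points at Day 19 (100 − 94.7) and 14.3 points at Day 21 (100 − 85.7). The effect on the mean cannot be estimated from the documents, because the number of late visits is unknown and zero is compatible with the plan. As pure illustration, in a safety analysis set of 100, each fully compliant participant seen on Day 21 lowers mean compliance by 14.3/100 = 0.14 points. If 0 to 10 participants were in that position (assumed), the mean would move by 0 to 1.4 points.

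The result assumes first intake on Day 1 and no supply beyond the one bottle. The 77.8% case in Step 4 is separate and arises within the permitted window.

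**What to change.** 1. In SAP 4.5.1, replace the denominator by min(18, max(14, date of final visit − date of first intervention intake + 1)). This is the 14-to-18 range the section already describes.
2. Count in the numerator only tablets taken up to Day 18, where eCRF exposure dates allow. Where only tablet counts exist, state the limitation: doses taken after Day 18 can mask earlier missed doses.
3. Reconcile Protocol 6.6.1 (Days 1 to 14) with Table 6-1 (14 days plus up to four), and state in the SAP how the planned tablet count follows from the reconciled text.

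Item 1 costs one SAP formula and one line of code, with no new data and no protocol amendment. Item 2 adds a short derivation from exposure data that the SAP already uses for treatment duration. Item 3 needs a clarification by the sponsor. Settling all three before database release avoids a decision on late visits made after the data are seen.

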6.8 Treatment of Overdose

In this study, an overdose is any dose higher than 5 mg vericiguat QD.

Limited data are available with regard to overdosage in patients treated with vericiguat. In the event of an overdose, hypotension may result. Symptomatic treatment should be provided. Vericiguat is unlikely to be removed by hemodialysis because of high protein binding.

In the event of an overdose, the investigator should:

- Evaluate the participant to determine, in consultation with the medical monitor, if possible, whether study intervention should be interrupted or whether the dose should be reduced.
- Closely monitor the participant for any AE/SAE and laboratory abnormalities
- Document the quantity of the excess dose as well as the duration of the overdose.

Decisions regarding dose interruptions or modifications following a suspected overdose will be made by the investigator in consultation with the medical monitor based on the clinical evaluation of the participant.

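### Can a participant who leaves before Day 14 score 100% compliance or more, contrary to SAP 4.5.1, and does the SAP need to change for it?

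*SAP*

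**What the plan says.** SAP 4.5.1 defines compliance as "number of tablets actually taken / number of tablets planned to be taken", times 100. It introduces the denominator with "It is 14 at least but considering the allowed extension by up to four days, the denominator will be calculated as", followed by the larger of 14 and the number of days from first intake to the final visit, both days counted. It then states that "Participants ending the study before day 14 will have a compliance below 100" per cent. Compliance is also tabulated as above, equal to or below 100%. The section does not name a data source for the numerator.

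The same section states: "The total intervention dose (according to drug accountability data from the eCRF) will be summarized in mg per day using descriptive statistics". It gives no divisor for the per-day figure. Treatment duration comes from a different source, the eCRF exposure data.

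Protocol 6.5 supplies the tablet rules. On supply: "A participant will receive exactly one bottle of vericiguat 5 mg tablets containing 18 tablets for any unforeseen events". On measurement: "Compliance will be assessed by counting returned tablets during the site visit". On tablets that do not come back: "Study intervention tablets not returned will be considered to have been taken unless otherwise specified". It also requires a reconciled record of the quantity each participant was given and took, intervention start and stop dates in the CRF, and a discussion and written explanation of any discrepancy in the count. SAP 4.1 plans no imputation of missing data.

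**The concern.** The SAP sentence carries no condition, and the only counting rule in either document can break it. The bottle holds four tablets more than the smallest denominator. A participant who takes a few doses, disappears and never returns the bottle would be credited with all 18 tablets, placed in the above-100% category, and given a total dose of 90 mg.

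SAP 4.1 reports the maximum, so one such case could set it. Protocol 6.8 states: "In this study, an overdose is any dose higher than 5 mg vericiguat QD". In a tolerability study of a starting dose, a maximum above 5 mg per day could be read as over-dosing when intake is simply unknown.

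A second doubt concerns the denominator, which includes the Visit 2 day. The schedule of activities (Protocol 1.3) asks for vital signs before intake and places tablet accountability at Visit 2. It does not say whether that day's dose is taken before the tablets are counted. If it is not, a fully adherent participant would appear as below 100%.

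**Working it through.** **Inputs.** 18 tablets of 5 mg per bottle (Protocol 6.5); one tablet a day (Protocol Table 6-1); denominator max(14, days from first intake to final visit, inclusive) (SAP 4.5.1). Anyone whose final visit falls before Day 14 has a denominator of 14.

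**Step 1: the SAP's own statement.** With documented intake of one tablet a day up to day d, compliance is d/14:

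- d = 1: 1/14 = 7.1%
- d = 7: 7/14 = 50.0%
- d = 13: 13/14 = 92.9%

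All are below 100%, so the sentence is reproduced.

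**Step 2: the Protocol 6.5 default as numerator.** With r tablets returned, compliance is (18 − r)/14:

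| Returned | Not returned | Compliance |
|---|---|---|
| 0 | 18 | 128.6% |
| 1 | 17 | 121.4% |
| 2 | 16 | 114.3% |
| 3 | 15 | 107.1% |
| 4 | 14 | 100.0% |
| 5 | 13 | 92.9% |

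The sentence then holds only if at least five tablets come back. Tablets not returned are those swallowed plus those kept or lost.

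**Step 3: dose per day.** An unreturned bottle is 18 × 5 = 90 mg. The divisor is an assumption, so the range is shown: 90/14 = 6.43 mg/day over the planned days, or 90/1 = 90 mg/day over a single documented intake day. With 100 participants and the other 99 at exactly 5 mg/day (also assumed), the mean is (495 + 6.43)/100 = 5.01 or (495 + 90)/100 = 5.85 mg/day. The upper figure requires an accountability total to be divided by exposure days, which the SAP does not call for.

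**Step 4: effect on mean compliance.** One participant in 100 scored 18/14 instead of 1/14 moves the mean by (128.6 − 7.1)/100 = 1.2 percentage points.

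**Step 5: the Visit 2 day.** If that day's dose is not taken before the count, an adherent participant seen on day d scores (d − 1)/d:

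- Day 14: 13/14 = 92.9%
- Day 15: 14/15 = 93.3%
- Day 16: 15/16 = 93.8%
- Day 17: 16/17 = 94.1%
- Day 18: 17/18 = 94.4%

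If it is taken first, the score is d/d = 100% throughout.

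**Step 6: who can reach step 2.** Participants who stop the drug stay in the study to Visit 2 (Protocol 7.1). Those who withdraw are to have an unscheduled visit where possible (Protocol 7.2), and the schedule lists accountability at that visit. At a visit the discrepancy must be discussed. Someone who leaves on Day 5 and returns 2 tablets would score 16/14 = 114.3% by the bare default, but 5/14 = 35.7% once intake is established. That leaves chiefly those lost to follow-up, who by Protocol 7.3 miss Visit 2 and cannot be contacted.

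**The case for a change.** The best case for a change is that the documents allow two programmers to treat the same participant differently. One could apply the Protocol 6.5 default and report 128.6%. The other could note that there was no count and that SAP 4.1 plans no imputation, and report a missing value. The SAP declares no departure from the protocol, so it cannot be said to have set the default aside. At one tablet a day intake cannot exceed the denominator, so the above-100% category can contain only genuine extra dosing or unreturned tablets, and a reader would want to tell those apart. The Visit 2 question does not depend on loss to follow-up and could touch many participants.

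Some of this stands. The numerator source and the mg-per-day divisor are not stated, and the sentence would be safer with a condition attached.

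It does not amount to an error. The formula asks for tablets actually taken, and Protocol 6.5 provides the records from which to establish that; its default applies only where nothing else is specified. Listings are planned, so an implausible value can be traced to a bottle that was never returned, and a maximum in a summary table does not classify anyone as overdosed. On the Visit 2 day, treatment from Day 1 through Day 14 (Protocol 6.6.1), the four-day extension in Protocol Table 6-1, the 18-tablet bottle and the added day in the denominator all fit counting that day. Only the order of count and dose is unstated, which is a matter of site procedure.

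**Conclusion.** No change to the plan is needed. The arithmetic is right: under the Protocol 6.5 default, 14 to 18 unreturned tablets over a denominator of 14 give 100.0% to 128.6%, so the SAP sentence can fail on that reading. On the reading its own formula suggests, documented intake of one tablet a day, it holds with a ceiling of 92.9%. The numerator source, the per-day divisor and the Visit 2 convention are details that analysts can settle sensibly from records the protocol already requires.

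The stakes are small. Descriptive compliance and mg-per-day summaries could shift for a group that is probably rare, though the documents give no frequency. One case in 100 moves mean compliance by 1.2 points, assuming only the Visit 1 dose was actually taken. The maximum could look odd, but its cause would be visible in the listings. Treatment duration rests on exposure data, and neither document derives the primary endpoint from the compliance ratio, so the trial's conclusion on tolerability does not depend on this point.

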#### 4.5.2 Adverse Events

All AEs will be summarized using the Medical Dictionary for Regulatory Activities (the current version at the time of analysis) PTs grouped by SOC.

Any medical occurrences/conditions that begin in the period between signing the informed consent form and the start of study intervention, and which are not related to a protocol-required study procedure, will be recorded as medical history/current medical conditions, not as AEs.

Any AEs related to study procedures recorded after signing of informed consent but prior to first treatment with study intervention will be considered as pre-treatment AEs.

AEs are considered to be treatment-emergent if they started or worsened after first administration of study intervention until completion of study for the respective participant. Therewith pre-treatment AEs and non-treatment-emergent AEs are equivalent and there are no post-treatment AEs defined in this study.

Symptomatic hypotension as assessed by the investigator is considered an adverse event of special interest in this study.

Individual listings of all AEs will be provided including AE onset and end date relative to start and end date of intervention and the duration of the AE. Listings of treatment-emergent as well as non-treatment emergent serious AEs, AEs with fatal outcome and deaths not attributed to AEs as well as AEs resulting in discontinuation will be provided in addition.

Overall summaries of the number of participants with any AEs, pre-treatment AEs, TEAEs and treatment-emergent AESIs, treatment-emergent AESIs restricted to moderate and severe intensity and deaths together with AEs with fatal outcome will be generated.

The number of participants with serious AEs, TEAEs, intervention related TEAEs TEAEs leading to discontinuation of study intervention, intervention-related TEAEs leading to discontinuation of study intervention, TEAEs by maximum intensity, intervention-related TEAEs by maximum intensity, non-serious TEAEs, serious TEAEs, intervention-related serious TEAEs, deaths together with AEs with fatal outcome and TEAEs with fatal outcome will be summarized using PTs grouped by SOC. Treatment-emergent AESIs and treatment-emergent AESIs restricted to moderate and severe intensity will be summarized using PTs.

An overview of TEAEs and serious TEAEs by demographic subgroups will be provided.

TEAEs leading to discontinuation will be summarized graphically by showing cumulative incidence estimates using Aalen-Johansen estimator.

In case of events with different intensity within a participant, the maximum reported intensity will be used. If intensity is missing, the event will be considered as severe. If the same event is reported as both unrelated and related to the study intervention within a participant, the event will be considered as related to study intervention. If the study intervention relationship is missing, the event will be considered as being related to the study intervention.

Version 1.0 Page: 13 of 15

